(11, 25) ESS usually includes uncinectomy, middle meatal antrostomy and opening of the bulla ethmoidalis. In polyposis, recurrent disease may be treated with progressively extended procedures. So far, there is inadequate evidence that total ethmoidectomy and removal of ethmoid cells below the skull base would be better than less extensive approaches. This is due to heterogenous patient samples and other methodological flaws of previous studies (11). Total ethmoidectomy with opening of other sinuses may be more efficient in reducing symptoms and revision rates in the severest form of CRSwNP. Preliminary results of our retrospective study indicate that patient history of oral corticosteroids and antibiotics for CRSwNP before surgery was related to uncontrolled disease in the follow-up. Furthermore, extended surgery seemed to decrease revisions rates. These factors in patient history and the extension of surgery related to uncontrolled disease need to be evaluated in a prospective randomized study design (31, 34). However, total ethmoidectomy combined with opening of other sinuses is potentially more susceptible to skull base, orbital and vascular complications. It is therefore usually only performed by experienced surgeons using navigation. Availability of experience, navigation and longer operation time are required when compared with limited approaches such as partial ethmoidectomy reaching posterior ethmoids. Recently, timing of surgery has been found to be important in the course of airway disease in CRS and asthma (11, 26). Prolonged uncontrolled disease may thus compromise treatment results. Therefore, early adequate surgery in the uncontrolled severe CRSwNP may prove cost effective.

A limited number of biomarkers are currently available the endotyping of CRS patients in clinical practise. Several potential biomarkers might be used: eosinophils in blood, total IgE, specific IgE (e.g. *Aspergillus fumigatus*, *Staphylococcus enterotoxin*), eosinophil cationic protein (ECP), eosinophil mucin or total IgE in nasal secretions, and periostin in serum (28-29).

Taken together, clinical trials as well as search for new genome-based markers and therapeutics are needed in attempt to hit early and to prevent permanent modulations of airway structure and function in patients suffering from severe CRSwNP, asthma and AERD.

2. Aims and significance of the study

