This is a randomized controlled multicenter study that focuses on severe CRSwNP \pm asthma \pm AERD. Our primary objectives of this study are to find out:

- (1) Does extended surgery (total ethmoidectomy with opening of large sinuses) reduce HRQoL more effectively than partial ethmoidectomy? The primary end-point is the disease-specific questionnaire SNOT-22. The secondary objectives are to:
 - 1) Evaluate the outcome of surgery on polyp size, symptoms, general HRQoL, asthma specific HRQoL, olfaction, nasal patency, revision-rate, exacerbation-rate, lung function, costs and safety
 - 2) Develop the care pathway of CRS+/-asthma+/-AERD patients to improve outcomes and cost effectiveness of treatment
 - 3) Develop safe, specific and sensitive genome-based biomarkers for detection and management models for of severe airway inflammation and to further develop markers for progressive disease forms.
 - 4) To see if patients with certain genetic and/or clinical predispositions will benefit from extended surgery.

Significance: The clinical significance of this study is to develop cost-effective treatment models that will facilitate risk-estimation and prevention of the onset and the progression of severe CRSwNP, asthma and AERD. The potential societal impact is that it reduces the burden of inflammatory airway diseases. It will increase co-work between

clinicians, standardize treatment protocols and increase equality in health care in Finland. The academic impact is to train PhD students and clinicians. We will publish in peer reviewed international open access medical journals.

3. Methods

A. Operative study

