The study is performed as a randomized prospective controlled multicenter trial. A total of 174 adult severe CRSwNP patients \pm asthma \pm AERD participate in the study. The patients are recruited at the Departments of Otorhinolaryngology and Head and Neck Surgery, Helsinki University Hospital (HUH) (n=60-80), Tampere University Hospital (TUH) (n=20), Kuopio University Hospital (KUH) (n=15), Oulu University Hospital (OUH) (n=20) and Turku University Hospital (Tyks) (n=15). Otorhinolaryngological department of the Academic Medical Center, AMC, Amsterdam will recruit 60-80 patients for the study. Patients refusing to participate in the study are asked to contribute with HRQoL data, and age and gender are recorded. The study will be monitored by a professional monitor. Electronic CRF and paper/electronic patient questionnaires provided by HUS will be used (eCRF and patient questionnaires, Granitics).

Power calculation: The mean postoperative difference in the Sinonasal Outcome test (SNOT-22) was assumed to be at least 9 between the treatment arms. In a previous study the response within each subject group was normally distributed with standard deviation 20. If the true difference in the experimental and control means is 9, we will need to study 79 experimental subjects and 79 control subjects to be able to reject the null hypothesis that the population means of the experimental and control groups are equal with probability (power) 0,8. The Type I error probability associated with this test of this null hypothesis is 0,05. Taking into account the patients lost to follow-up, 10%, the number of patients needed to recruit is 174.

The diagnosis of CRS with nasal polyps (NP) is based on positive history, nasal endoscopy and computed tomography scans (EPOS 2012). EPOS-criteria for CRS include: Inflammation of the nose and the paranasal sinuses characterised by two or more symptoms, one of which should be either nasal blockage/obstruction/congestion or nasal discharge (anterior/posterior nasal drip): \pm facial pain/pressure, \pm reduction or loss of smell.

[figure not shown]
The diagnosis of asthma is based on spirometry, methacholine or histamine challenge and peak expiratory flow (PEF). Allergy is verified with positive history and skin prick test or specific igE. AERD is verified by typical history.

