We also monitor intra-operative factors (such as anesthesia method, use of local e.g. cocaine, terracortril and systemic medication, e.g. antibiotics and dexametasone, operation time and bleeding, use of tampons, complications, mucopurulent excretions, early postoperative factors such as duration of hospitalization, timing of tampon removal, duration of sick leave, medication, complications, visits and hospitalizations; as well as exacerbations, need of medication (po. corticosteroids; antibiotics). Time of surgery and equipment needed is recorded.

The primary end point is the change in SNOT-22 1 and 2 years postoperatively. Secondary end points include changes in polyp score, LM CT score, hrQOL, loss of productivity, nasal patency (peak nasal inspiratory flow (PNIF) +/- acoustic rhinometry (ARM), olfaction test (Sniffin' Sticks, identification), lung function (spirometry and PEF) and pathologic findings. Safety (complications, adverse effects) costs and loss of productivity between study arms will be compared. The study will compare costs of CRSwNP and asthma treatment one year before and two years after surgery. In addition to data from medical records and patients, data may be collected from national health records.

During and after follow-up, patients can undergo revision operation or other treatment, if needed and patients will still be followed for the duration of the study. Patient's disease control is monitored postoperatively by ENT-doctor as described earlier. Patients who have uncontrolled disease not responding to medication undergo CT scans and are evaluated for the need of removal of polyps and re-ethmoidectomy according to their study arm. In addition, AERD-patients are evaluated for their willingness in ASA desensitization and to participate in the AirGOs clinical trial.

B. Genome-scale search for biological key-factors

Peripheral blood, intranasal mucus and cell brushing samples, nasal polyp and/or nasal mucosal biopsies are taken from clinical trial participants and volunteer control subjects. The samples will be stored at Helsinki Biobank. These samples are collected in a time-series manner (pre-intervention, 24w post start of intervention) and biopsies are taken under local anesthesia. Nasal brushings and mucus swabs are collected from nasal mucosa, under middle turbinate, without local anesthesia. If possible, subjects are asked to be for 7-14 days without CRS medication before taking nasal specimens.

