Statistics. Data analysis will be carried out on the relationship between two operative treatments, and between ASA- and placebo desensitization. Variables tested in the statistical models include age, gender, exposures, infections, diseases, symptoms, exacerbation-rate, satisfaction, image-findings, endoscopic findings, operation, perioperative factors (such as operation time), complications, sick leave, biological factors (predisposing SNPs, alterations in transcriptome or microbiome), occupation, asthma, grade of nasal polyps, AERD, allergy, revision-rate, side-effects of AD, hospitalizations, sick leaves, and other factors at different time-points. We will use several software: R 3.0.2, SPSS 22.0 Statistical Software Package (SPSS, Chicago, IL) and STATA (Release 13.1 software, StataCorp, Texas, USA). For comparisons, the results will be analyzed by Logistic regression, Student's t-, Chi-square, (nonparametric) Fisher's exact and Mann Whitney U test, Cox's proportional-hazards model, cumulative hazard function H(t), hazard ratio, Kaplan–Meier method, and log rank test. Genetic calculations on Hardy–Weinberg equilibrium and linkage disequilibrium will be performed with Arlequin (version 3.5) using SPSS Statistics (version 20.0, IBM). P-values less than 0.05 are considered statistically significant. Results of logistic regression are reported as odds ratios (OR) with 95% confidence intervals. All models will be adjusted by selected covariates (potential confounding factors).

4. Implementation of the study plan

The **operative** trial will be performed during the years 1-5, starting in September 2018. The wetlab will be performed during the years 2-6. The statistical analyses, data management, search for literature, and manuscript(s) will be performed during the years 1-6.

5. The study group and collaborators

The study group:

Docent, Otorhinolaryngologist (HUH) [name] is director and is responsible for the management of the project and conducts the AirGOs Operative study in ENT hospital of HUH.

Docent, Pulmonologist (HUH) [name], is vice-director and conducts pulmonological assessment in Skin and Allergy Hospital (HUH/IAS).

MD, PhD, Otorhinolaryngologist (HUH) [name], is vice director and performs operative and clinical study in ENT Hospital

Docent [name] (HUH) performs in IAS and conducts data management, manuscripts and sample studies

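### The plan assigns no test or estimate to complications, so a 5 versus 0 split could be called significant or not, and absolute excess risk is never estimated

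*Combined protocol and SAP*

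**What the plan says.** The background section, on extent of surgery, states that "total ethmoidectomy combined with opening of other sinuses is potentially more susceptible to skull base, orbital and vascular complications". Section 2 (Aims) includes safety in the first secondary objective, at the end of a list that closes with "revision-rate, exacerbation-rate, lung function, costs and safety". Section 3.A (Operative study) provides for recording complications during and after surgery and then says: "Safety (complications, adverse effects) costs and loss of productivity between study arms will be compared".

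The Statistics paragraph in section 3 includes complications among the variables for the models. On methods it says "the results will be analyzed by Logistic regression, Student's t-, Chi-square, (nonparametric) Fisher's exact and Mann Whitney U test", followed by survival methods. It does not say which method applies to which outcome. The criterion is "P-values less than 0.05 are considered statistically significant", with no statement of one- or two-sided testing. The one interval promised is "Results of logistic regression are reported as odds ratios (OR) with 95% confidence intervals".

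The power calculation in section 3.A rests on SNOT-22 alone: "we will need to study 79 experimental subjects and 79 control subjects", and after allowance for loss to follow-up, "the number of patients needed to recruit is 174".

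The text available for review contains no definition or grading of a serious complication, no risk difference, no safety margin and no comment on power for safety.

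**The concern.** The trial should help decide whether to extend surgery in severe nasal polyposis. That means weighing a SNOT-22 gain against rare but serious complications, so the reader needs the absolute excess risk and how large an excess the data still allow.

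The plan does not secure that. For a yes/no outcome it offers three methods and one threshold. With few events these methods disagree near the threshold, so the same data could be reported either way by a choice made after they are seen. The promised odds ratio fails when an arm has no events, and where it exists it does not state an absolute excess. Whichever test is used, a non-significant result would be the likely outcome even under a several-fold increase in risk.

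**Working it through.** **Inputs.** From the documents: 79 evaluable per arm; 174 recruited, so 174/2 = 87 per arm if allocation is equal; threshold 0.05. Assumed: two-sided tests, and complication rates chosen for illustration, because the documents give none.

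**The plan's own figure.** For a difference of 9 and SD 20, the normal approximation gives n = 2(1.960+0.842)² × 20²/9² = 2 × 7.85 × 400/81 = 77.5, so 78 per arm. The t distribution gives 79 (power 0.803 at 79, 0.797 at 78). Then 158 × 1.10 = 173.8, so 174. The stated size reproduces, and nothing in it concerns safety.

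**One result, several verdicts.** Take 5/87 (extended) versus 0/87 (control).

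- Fisher's exact: the one-sided probability is C(87,5)/C(174,5) = 0.0295. With equal arms the two-sided value is double, p = 0.059.
- Uncorrected chi-square: 174(5×87)²/(87×87×5×169) = 5.15, p = 0.023.
- Chi-square with Yates correction: 174(435−87)²/(87×87×5×169) = 3.29, p = 0.070.

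At 79 per arm the three values are 0.059, 0.023 and 0.069. The smallest expected count is 5/2 = 2.5, where Fisher is the usual choice, but the plan does not say so. With no control events, Fisher first falls below 0.05 at 6 versus 0 (p=0.029) and uncorrected chi-square at 4 versus 0 (p=0.043). With one control event the thresholds are 8 versus 1 (p=0.034) and 7 versus 1 (p=0.030).

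**What estimation would show.** For 5/87 versus 0/87 the risk difference is 5/87 = 5.7 points. The Wilson 95% limits are 2.48% to 12.76% for 5/87 and 0% to 4.23% for 0/87. Newcombe's method gives:

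- lower limit: 5.75 − √[(5.75−2.48)² + 4.23²] = 0.4 points
- upper limit: 5.75 + (12.76−5.75) = 12.8 points

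For 4/87 versus 1/87, Fisher gives p=0.37, while the Newcombe upper limit is 10.2 points. For an arm with 0/87, the exact two-sided 95% upper limit is 1 − 0.025^(1/87) = 4.2%.

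**How often a real excess would be missed.** Exact enumeration of two binomials at 87 per arm, counting only rejections in the direction of harm:

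| Assumed control v extended | Missed by Fisher | Missed by uncorrected chi-square |
|---|---|---|
| 0.5% v 2% | 99.5% | 94% |
| 1% v 3% | 98% | 88% |
| 1% v 5% | 86% | 68% |
| 2% v 6% | 87% | 76% |
| 5% v 10% | 84% | 77% |

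**The odds ratio.** With no events in one arm the maximum-likelihood odds ratio is zero or infinite. The chance of no control events is (1−p)^87: 0.995^87 = 65% at a rate of 0.5%, and 0.99^87 = 42% at 1%.

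**The case against.** Several counter-arguments have weight.

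- A reader might infer that 5 versus 0 would necessarily be reported as no significant difference. The documents do not support that. Fisher is not assigned to complications, and uncorrected chi-square, also listed, gives p=0.023. What stands is that the verdict is undetermined.
- A reader might infer that safety is judged by tests alone. It is not: odds ratios with 95% intervals are promised, and complications are among the model variables. At an assumed 1% control rate the control arm has at least one event 58% of the time (100% − 42%). Even with none, a profile-likelihood interval can be computed; for 5/87 versus 0/87 its lower limit for the unadjusted odds ratio is about 2.2. The plan does not provide for this, and an odds ratio still does not give the absolute excess.
- A reader might infer that the sponsor expects more complications. The background calls them a potential risk, and it adds that such surgery is usually left to experienced surgeons with navigation. Section 3.A likewise says extended surgery is usually navigated.
- Nothing in the plan equates p≥0.05 with safety. The 0.05 rule is a general convention covering every analysis, and safety is secondary.
- Low power for rare harms is unavoidable with 174 patients, and estimation does not change it. That is true, but an interval makes the remaining uncertainty visible, which a non-significant p-value does not.

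**Conclusion.** The point holds in a limited form. The plan leaves the analysis of complications open on the harm it singles out, and it secures no estimate of absolute excess risk. The choice among listed tests alone moves a 5 versus 0 result from p=0.023 to p=0.059 (0.070 with Yates correction). Low sensitivity does not depend on choosing Fisher: over the assumed rates, uncorrected chi-square misses 68% to 94% of real excesses and Fisher 84% to 99.5%.

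These miss rates rest on assumed event rates, two-sided testing and 87 per arm. The 5 versus 0 comparison needs no assumed rate and is almost the same at 79 per arm. It would go too far to say that the plan will declare extended surgery safe: no such rule is written. This is a worthwhile, inexpensive improvement to a secondary analysis and does not affect the SNOT-22 comparison.

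**What to change.** In the Statistics paragraph, make estimation the main safety analysis:

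- Define serious complications (skull base, orbital, vascular). For these, and for any complication, report counts per arm and the risk difference, extended minus control, with a 95% Newcombe interval or a similar score or exact interval. State the upper limit as the largest excess risk not excluded.
- For an arm with no events, give its exact upper limit (4.2% for 0/87), and do not rely on an unpenalised logistic odds ratio.
- If a p-value is also reported, name Fisher's exact test in advance and state that p≥0.05 will not be read as comparable safety.

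Do not write a fixed detectable excess, such as 10 percentage points, into the plan: any such figure depends on the test and on an assumed control rate that the documents do not supply.

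The cost is a few sentences. Complications are already recorded, so no extra data or patients are needed. The downside is a less reassuring safety statement and no yes/no verdict on safety.

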Adult patients with severe CRSwNP \pm asthma \pm AERD are recruited. Clinical baseline information of the patients is collected including smoking, allergy, asthma, medication, previous operations, co-morbidities, duration of symptoms. During preoperative visit/s in the ENT clinic nasal medication including treatment of exacerbations during the previous year is recorded. Medication for asthma during the previous year is counted and emergency care visits for airway symptoms/asthma attacks, hospitalizations, and other visits for asthma are monitored.

Preoperatively the patients undergo endoscopy (35) and (CB)CT. Polyps are scored on a 0-4 scale on each side and a Lund-Mackay computer tomography score (LM CT score, range, 0-24) is obtained (30, 31). Quality of life data and data for cost analysis are collected by validated questionnaires: Sinonasal outcome test (SNOT-22), generic HRQoL questionnaires (15D, EQ-5D-5L). Work Productivity and Activity Impairment Questionnaire: General Health (WPAI:GH), Productivity Costs Questionnaire (iPCQ), Medical Consumption Questionnaire (iMCQ) and asthma control tests (ACT,

miniAQLQ). The patients undergo spirometry with bronchodilatation and PEF (2 weeks as a diagnostic test, 1 week in follow-up with patients own medication).

Figure 1.

Inclusion criteria: Patients having uncontrolled CRSwNP and not responding to medical treatment are asked to participate in the study. Conservative treatment consists of corticosteroid drops and nasal lavage lasting at least 3 months before surgery is considered. Uncontrolled CRSwNP is defined as high polyp grade (≥ 4 , bilateral), and SNOT-22 ≥ 30 , and high CT Lund-Mackay score (LM score ≥ 14). In addition, patient should have a history of at least one of

the following: ≥ 1 previous surgeries for CRSwNP; ≥ 1 oral corticosteroids during the past two years; ≥ 3 antibiotic courses during the past two years. In patients with contraindication/adverse effects in using oral steroids additional criteria are not required.

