Exclusion criteria: Age < 18 years, age > 65 years, complication of CRS (f.e. mucocele, invasive fungal rhinosinusitis), other diagnosis than CRSwNP (inverted papilloma, antrochoanal polyp etc), previous external sinus surgery or Draf 3 procedure (or indication for external approaches or Draf 3, bleeding diathesis, pregnancy/ breastfeeding, cystic fibrosis, primary ciliary dyskinesia (PCD), sarcoidosis, granulomatosis with polyangiitis (GPA), eosinophilic granulomatosis with polyangiitis (EGPA), immunosuppression (diagnosed Specific Antibody Deficiency (SAD), CVI, HIV or use of biologicals/immunosuppressive medication), immunotherapy, daily use of systemic corticosteroids, communication problems (f.e. neurological/psychiatric disease, language skills), unlikely to comply, other severe disease, inability to be operated.

Randomization and surgery. The randomisation is performed by a professional statistician in blocks and for each center. The randomisation group of consecutive patients is sealed in numbered envelopes and kept in a locked room; the envelope is opened during the visit after informed consent. The patients are randomized for 1. total ethmoidectomy +sphenotomy +frontal opening (Draf2a) and 2. removal of polyps with uncinectomy, +/-opening of the natural ostium +/- ground lamella but not opening sphenoid or frontal sinus unless already opened in a previous surgery (Figure 1). Sinus operations are performed under general or local anesthesia on both sides with standard techniques and instrumentation by ENT specialists. Videoendoscopy is recorded at completion of extended surgery. Extended sinus surgery is usually performed with navigation. If not contraindicated, the patients may receive peroral corticosteroids 10-14 days perioperatively starting a few days before surgery.

Follow-ups. Patients are monitored before and during the follow-ups. The follow-ups are 3, 6, 9, 12,18 and 24 months postoperatively. During each visit the validated questionnaires and nasal endoscopy are performed. Nasal patency and olfaction as well as spirometry and PEF are monitored. Blood and tissue samples and low-dose sinus CT scans (1 year postop) are performed (Figure 1).

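### The before-after cost comparison sets one year against two without a per-year unit, and the randomised cost comparison does not name prior-year cost as a covariate

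*Combined protocol and SAP*

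**What the plan says.** Two cost comparisons appear next to each other in the end-points paragraph of section 3 A (Operative study). The first is between the randomised arms: "Safety (complications, adverse effects) costs and loss of productivity between study arms will be compared". The second is before against after: "The study will compare costs of CRSwNP and asthma treatment one year before and two years after surgery".

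The same section describes the data behind them. Before surgery, "nasal medication including treatment of exacerbations during the previous year is recorded" and "Medication for asthma during the previous year is counted". After surgery, "The follow-ups are 3, 6, 9, 12,18 and 24 months postoperatively". Both arms are operated: "The patients are randomized for 1. total ethmoidectomy +sphenotomy +frontal opening (Draf2a) and 2. removal of polyps with uncinectomy". On entry, "Patients having uncontrolled CRSwNP and not responding to medical treatment are asked to participate in the study".

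The Statistics paragraph makes the two operations the analysis contrast. For comparing a continuous outcome between groups it lists Student's t-test and the Mann-Whitney U test. It also promises in general terms that models will be adjusted for covariates still to be selected. Cost in the year before surgery is not in its list of variables. Nowhere does the plan say whether costs are totals or per year, whether the index operation is included, or how costs are analysed.

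Section 2 lists costs and cost effectiveness among the secondary objectives, and cost-effective treatment models under significance.

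**The concern.** Three separate matters arise.

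- **Units.** The pre-operative window is 12 months and the post-operative window is 24. Without a per-year unit, an analyst who follows the sentence literally compares quantities that differ by a factor of two even when nothing has changed.
- **Control.** The before-after contrast is within patients, and no group goes unoperated. Patients enter when their disease is uncontrolled, so later costs may fall with no effect of either operation.
- **Precision.** The randomised comparison is the one that can support a conclusion about the two operations. The plan intends to have each patient's prior-year cost but does not say that it will be used there.

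What is at stake is how the cost results can be read, and the width of the interval around the between-arm cost difference. The primary end point, SNOT-22, is not affected.

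**Working it through.** The plan gives no cost figure, so there is none to reproduce. The calculation below shows only what the stated windows imply.

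**Inputs.** From section 3 A: 1 year before, 2 years after, visits at 12 and 24 months. Assumed, because the documents give no costs: annual cost before surgery = 1 unit; proportional annual saving s from 0 to 75%; one-off cost of the index operation c from 0 to 1 unit.

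**Step 1: effect of the windows.** Raw two-year total = 2(1 - s) + c, set against 1. Per-year figure = [2(1 - s) + c] / 2, set against 1. With c = 0:

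| True annual saving s | Raw total after (before = 1) | Apparent change | Per year after |
|---|---|---|---|
| 0% | 2.00 | +100% | 1.00 |
| 10% | 1.80 | +80% | 0.90 |
| 25% | 1.50 | +50% | 0.75 |
| 50% | 1.00 | 0% | 0.50 |
| 75% | 0.50 | -50% | 0.25 |

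On raw totals any saving below 50% looks like an increase. Per year, each saving appears at its true size.

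**Step 2: the index operation.** On raw totals, break-even is where 2(1 - s) + c = 1, so s = (1 + c)/2: 50% at c = 0, 75% at c = 0.5, 100% at c = 1. Per year, break-even is where [2(1 - s) + c]/2 = 1, so s = c/2: 0% at c = 0, 25% at c = 0.5, 50% at c = 1. The per-year break-even reflects a real cost and not a window artefact, but it shows that including or excluding the operation changes the answer.

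**Step 3: selection on uncontrolled disease.** Suppose patients enter with cost z standard deviations above their long-run level, and cost in adjacent periods has correlation ρ. The expected fall without treatment is (1 - ρ)z. With assumed ρ from 0.3 to 0.7 and z from 0.5 to 1.0, the smallest fall is (1 - 0.7) × 0.5 = 0.15 SD and the largest is (1 - 0.3) × 1.0 = 0.70 SD. This works against the window effect of step 1. The documents give nothing from which to net the two.

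**Step 4: the between-arm comparison.** Let the arms' mean annual costs after surgery be A and B. Over 24 months the difference is 2A - 2B = 2(A - B). The windows are the same in both arms, so the ratio of one year to two introduces no bias.

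**Step 5: adjusting for prior-year cost.** If prior-year and follow-up cost have correlation r, adjustment multiplies the variance of the between-arm difference by about 1 - r². At r = 0.3 this is 1 - 0.09 = 0.91, a fall of 9%. At r = 0.5 it is 1 - 0.25 = 0.75, a fall of 25%. Standard errors are multiplied by √0.91 = 0.95 and √0.75 = 0.87. The range for r is an assumption.

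**The case against.** The strongest reply is that the sentence on costs may only describe the periods for which data are gathered. It never says that raw totals will be compared. Cost per year, or the year before against each later year, fits the same words, and the 12- and 24-month visits make an annual split possible. This stands. A reader might infer that the cost analysis is wrong as written, but the documents show only that the unit is unstated.

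A reader might also infer that the cost results as a whole are compromised. They are not: the preceding sentence plans a randomised comparison in which both arms share the same windows.

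A third tempting inference is that lack of a control group is a further reason why a real saving could be hidden. The documents point the other way. Selection on uncontrolled disease would tend to lower later costs and overstate a saving.

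On baseline adjustment, the reply is that the general sentence on covariates does not exclude prior-year cost, and that randomisation already makes the unadjusted comparison unbiased. Both statements are true. But the covariates are not named, and neither of the tests listed for a continuous outcome adjusts for anything. The logistic and Cox models also listed do not analyse mean cost. The gain is therefore in precision and is not secured by the present text.

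Finally, the one-year look-back is explicit for nasal medication, exacerbation treatment and asthma medication. It is less clear for asthma visits and hospital stays, and is not stated for sinus-related visits or lost productivity. National records are only a possible source. This limits how complete a prior-year cost can be, but does not prevent use of the components that are recorded.

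**Conclusion.** The point holds as a gap in specification plus a free improvement. The before-after contrast has unequal windows and no stated unit. If raw totals were used and the index operation omitted, unchanged annual cost would show as +100%, and only an annual saving above 50% would show as a fall. Those figures depend on that reading, which the text neither adopts nor rules out. Because regression to the mean acts in the opposite direction, the net direction of error is undetermined, and the contrast can bear no more than a descriptive interpretation.

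The between-arm comparison is unbiased with respect to the windows. Adjusting it for prior-year cost would cut its variance by about 9% to 25% if r lies between 0.3 and 0.5; no cost data in the documents support or contradict that range. The matter is minor: costs are a secondary objective.

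**What to change.** Replace the before-after cost sentence in section 3 A, and add the method to the Statistics paragraph, along these lines:

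*The main cost analysis is the between-arm difference in mean cost per patient over 24 months after surgery, estimated in a regression model adjusted for cost in the year before surgery. Where the pre-operative record is incomplete, the adjustment uses the cost components recorded for that year. Costs before and after surgery are also reported descriptively, per patient-year, with the year before surgery set beside post-operative year 1 and year 2 separately. The cost of the index operation is shown separately.*

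The text should also say whether the index operation and any revisions are included in the 24-month total.

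This changes wording only, and should be settled before costs are analysed. It needs no additional patients or visits. The adjustment relies on the prior-year data that the trial already plans to obtain. If a fuller prior-year cost is wanted than the explicit look-back gives, the missing components would have to come from medical or national records, which the plan already allows as sources.
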